8.2.3. Reporting of Deaths

All deaths, including death due to disease progression, occurring from the time the ICF is signed through the Safety Follow-up Period (30 days after the last dose of study drug or discontinuation, whichever is earlier) must be reported as an SAE on a paper SAE form **within 24 hours** from the time the Investigator first becomes aware of the death.

Death is not an acceptable AE/SAE term; death is an outcome of an SAE. When reporting a death, site personnel will be required to identify which of the following best describes the category for cause of death:

- Toxicity caused by study drug
- Disease progression
- Clinical disease progression
- Other causes

8.2.4. Follow-up of Serious Adverse Events

When an SAE occurs, the Investigator will promptly take appropriate measures and follow up with the patient until the earliest occurrence of one of the following:

- The SAE has resolved
- The SAE has stabilized; an SAE can only be considered "stabilized" if the clinical manifestation or laboratory results being followed/assessed has remained constant (is not worsening) based on the Investigator's medical judgement.
- Start of new antitumor therapy
- Death

8.3. Disease Progression

Disease progression is not an acceptable AE term. In cases of non-fatal disease progression, the relevant symptom(s), sign(s), and complication(s) that led to the diagnosis of clinical disease progression should be reported as AE(s). If the relevant symptom(s), sign(s), and complication(s) meet any of the serious criteria, they should be reported as SAE(s). In both cases it should be indicated whether the symptom(s), sign(s), and complication(s) are related to clinical disease progression.

In cases of death due to clinical disease progression, the relevant major symptom(s), sign(s), and complication(s) that led to the death should be reported as SAE term(s). Clinical disease progression may only be reported as an SAE term if none of the relevant symptoms, signs, or complications supports a fatal outcome.

8.4. Laboratory Assessments

8.4.1. Reporting and Evaluation of Laboratory Test Results

All laboratory results must be reviewed by the Investigator. A new laboratory or instrumental abnormality that has a clinical impact on a patient (including eg, resulting in study drug dose reduction, treatment delay, treatment discontinuation or requirement of intervention) is considered an AE, unless it is considered part of clinical manifestations to a clinical diagnosis that is already reported as an AE.

All laboratory values that are out of the normal range are to be evaluated for their clinical impact before exposing the patient to the next dose of TAS-120. The laboratory must provide normal reference ranges.

The NCI-CTCAE Version 5.0 will be used to grade the severity of laboratory data.

8.4.2. Repeat Testing

Evaluation of any clinically significant laboratory test will be repeated, as clinically indicated, until the value returns to the baseline level or clinically stabilizes, or until another treatment is given.

8.5. Other Safety Information

8.5.1. Pregnancy

If a patient becomes pregnant while on study treatment or within 30 days following the last dose of study therapy, the study treatment must be immediately discontinued if ongoing. Pregnancy information in a female patient (or for the female partner of a male patient) should be reported **within 24 hours** from the time the Investigator first becomes aware of a pregnancy or its outcome. This should be performed by completing a paper Pregnancy Form and faxing or e-mailing it to Sponsor's Pharmacovigilance group or its designee.

New and/or corrected information regarding the pregnancy obtained after submitting the Pregnancy Form must be submitted on an updated Pregnancy Form to the Sponsor's Pharmacovigilance group or its designee.

If the outcome of the pregnancy is a stillbirth, congenital anomaly/birth defect, or a serious event in the mother, it should be reported as a SAE to the Sponsor's Pharmacovigilance group or its designee. Live births will be followed up by the Investigator. Any information that may be associated with the study drug should be reported even after study completion.

8.5.2. Overdose

An overdose for this clinical study is defined as taking an intentional or unintentional dose of TAS-120 or fulvestrant beyond the recommended dose for 1 day or beyond the recommended total dose in each cycle.

An overdose of TAS-120 or fulvestrant should be reported as an AE, and must be recorded on the SAE form and/or eCRF (or other specified report form) and reported to the Sponsor's Pharmacovigilance group or its designee **within 24 hours** from the time the Investigator first becomes aware of the overdose, whether or not it was accidental or intentional, and whether or not the patient developed an AE (even if not fulfilling a seriousness criterion).

An accidental or intentional overdose of concomitant medication should only be reported if it is associated with an AE

There is no known antidote available in case of TAS-120 or fulvestrant overdose. Overdose should be managed with close monitoring and administration of prophylactic and symptomatic therapies to prevent or correct potential side effects.

8.5.3. Medication Errors

A medication error for this clinical study is defined as any unintentional error in prescribing, dispensing, or administering the study drug while the study drug is in the control of the healthcare professional or patient.

Please refer to the current eCRF Completion Guidelines for the details regarding reporting of medication errors to the Sponsor's Pharmacovigilance or designee.

The following types of medication errors, regardless of whether it is associated with an AE or SAE, should be reported to the Sponsor's Pharmacovigilance or designee within 24 hours of first awareness from the time the Investigator first becomes aware of its occurrence, using the SAE form and/or eCRF (or other specified report form):

- Medication errors with study medication or concomitant medication resulting in an AE
- Medication errors with study medication resulting in an overdose
- Incorrect route of study medication administration
- Administration of the incorrect study medication

Note: Medication errors with the study medication that result in the omission of an administration, an incorrect dose, or the administration of more than the prescribed dose (but does not meet the overdose criteria), will not be reported as a SAE, but will be identified through the recording of study drug accountability data in the eCRFs.

9. PHARMACODYNAMIC AND PHARMACOKINETIC EVALUATION

9.1. Pharmacodynamic and Biomarker Assessments

9.1.1. Objectives and Background

Exploratory objectives of this study are to assess the downstream pharmacodynamic effect of TAS-120 in single-agent and/or combination therapy and to explore markers of response and mechanisms of resistance to TAS-120 in tumor tissue biopsies and/or in ctDNA. These exploratory assessments of biomarkers include but are not limited to:

- Any *FGFR* aberrations
- p-AKT
- p-MAPK
- Ki67

All biomarker assessments described in this section will be performed at the timepoints shown in the Schedule of Events (Table 1); methods of sample collection and preparation will be described in a separate Laboratory Manual.

The pharmacodynamic biomarker population will consist of all patients who received TAS-120 and have evaluable pharmacodynamic biomarker data. Detailed analytical procedures will be described in the SAP.

9.1.2. Assessment of *FGF/FGFR* Aberrations in Blood

A blood sample will be collected to assess *FGF/FGFR* aberrations in ctDNA prior to the first TAS-120 administration on Day 1 of Cycle 1, on Day 1 of each alternative uneven cycle (Cycle 3, 5, 7 and ongoing), at time of disease progression, and at the EOT visit. Blood will be collected at each time point. This sample is being collected for exploratory analysis to evaluate *FGF/FGFR* aberrations in circulating blood and for future clinical development.

9.1.3. Tumor Biopsy

Archival or fresh tumor biopsy samples will be collected during the screening period to retrospectively confirm FGFR gene status at the Sponsor's designated central laboratories. The remaining samples may be stored at the Sponsor's designated central laboratories for up to 10 years for future testing.

Optional pre- and post-treatment tumor biopsies for pharmacodynamic assessment will be collected from patients who consent at Baseline, at the end of Cycle 1 (Cycle 1 Day 28 ± 7 days), and at the time of disease progression. These samples are being collected for exploratory analysis to evaluate the changes of downstream protein activation and other markers that may be associated with response and/or development of resistance to TAS-120 in tumor tissues.

9.2. Population Pharmacokinetic Sample Collection and Analysis

Blood samples will be collected for PopPK analysis including estimation of steady-state exposure such as AUC. The samples will be used to determine concentrations of TAS-120 in plasma.

Total of three PK samples will be collected on Cycle 2, Day 1 (C2D1), within 1 hour prior to dosing and at 2 hours (±1 hour) and 5 hours (at least 3 hours apart from sampling at 2 hours) post-dose. The 3 samples should be collected on the same day. A pre-dose sample may be collected again in case the patient interrupted medication after the pre-dose sample was collected and had C2D1 at a later date. The second pre-dose sample will be recorded as pre-dose sample for C2D1. Dates and times of each sample collection must be recorded.

Details on the collection and preparation of plasma samples will be provided in a separate Laboratory Manual. Detailed analytical procedures will be described in the independent SAP for PopPK.

10. STATISTICS

The statistical analysis methods will be documented in detail in the SAP.

10.1. Estimation of Sample Size

Up to 168 patients in total may be enrolled in the study.

Please note: the patient numbers given for efficacy analysis are for the response-evaluable population, defined as the subset of treated patients who have measurable disease (or evaluable disease in Cohort 3), who have at least 1 post-baseline disease/tumor assessment, and who have centrally confirmed *FGFR* amplification (Table 13). If a treated patient is not eligible for the response-evaluable population (for example, because *FGFR* amplification cannot be centrally confirmed or no post-baseline tumor assessment is available), additional patients will be enrolled to ensure the correct number of response-evaluable patients for analysis as described below.

Sample size considerations for **Cohorts 1 and 2** (primary endpoint ORR) are based on a 2-stage Optimal Simon design, comparing a poor response of \leq 15% versus a promising response of \geq 30%, at an approximate 5% 1-sided significance level and 80% power.

- In Stage 1 (futility assessment), enrollment will include 19 patients in each cohort and accrual will continue to Stage 2, if at least 4 (21%) of 19 patients respond (CR or PR).
- In Stage 2, if the Stage 1 futility boundary is exceeded, an additional 36 patients will be enrolled, for a total of at least 55 patients per cohort. In Cohorts 1 or 2, with a total of 55 patients, if the observed ORR is 30.9%, the 95% exact confidence interval (CI) is (19.1%, 44.8%).

Sample size considerations for **Cohort 3** (primary endpoint CBR) are also based on a 2-stage Optimal Simon design. The null hypothesis that the true CBR is 25% will be tested against a 1-sided alternative, which yields a type I error rate of 5% and power of 80% when the true CBR rate is 50%. In the first stage, 9 patients will be treated. If there are \leq 2 patients with clinical benefit (ie, CR or SD \geq 24 weeks) in these 9 patients, the cohort will be discontinued. Otherwise, 15 additional patients will be treated for a total of 24 patients. The null hypothesis will be rejected if \geq 11 patients with clinical benefit are observed in 24 patients.

Sample size considerations for **Cohort 4** (primary endpoint 6-month PFS) are based on a proof-of-concept Phase 2 design, differentiating a null 6-month 25% PFS rate with a target rate of 50%. Approximately 28 patients will be treated. It has approximately 80% power to reject the null hypothesis that the true 6-month PFS rate is \leq 25%, considering a 1-sided alpha (type 1 error rate) of 5%. In addition, 6-12 patients will be enrolled as a safety lead-in. The patients in the safety lead-in who are treated at the recommended Phase 2 dose will be included in the main cohort of 28 patients. Thus up to 34 patients may be enrolled for this cohort.

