10.3. Analysis Populations

The analysis study populations in this study are defined in Table 13.

Table 13: Analysis Populations

Analysis Population	Definition	
All Enrolled Population:	All patients enrolled in this study	
All Treated Population/Full Analysis Set:	All enrolled patients who received at least 1 dose of study drug	
DLT Evaluable Set:	All patients in the All Treated Population in Cohort 4, excluding those for whom the cumulative dose of TAS-120 was <75% and/or the cumulative dose of fulvestrant was <100% for reasons other than DLTs in Cycle 1, or who received prohibited concomitant medications or therapies	
Response Evaluable Set:	All patients in the All Treated Population who meet Inclusion Criterion #4, have measurable disease (or evaluable disease in Cohort 3), who have at least 1 post-baseline disease/tumor assessment, and have centrally confirmed FGFR amplification. Patients who discontinue due to intolerable toxicity or death prior to the first post-baseline tumor assessment will also be considered evaluable and will be classified as non-responders.	
PopPK Evaluable Set:	All patients in the All Treated Population who have evaluable plasma TAS-120 concentration data for analyses	
Pharmacodynamic/Biomarker Evaluable Set:	All patients in the All Treated Population who have evaluable pharmacodynamic/biomarker data for analyses	

Abbreviations: DLT=dose-limiting toxicity.

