The exact 2-sided 95% CI based on Clopper-Pearson methodology will be derived for ORR. The null hypothesis will be rejected if at least 15 responders observed out of 55 patients. If 17 responders observed out of 55 patients, the ORR is 30.9% and the 95% exact CI is (19.1%, 44.8%).

CBR (Cohort 3) will be calculated based on the best overall response. Because patients in Cohort 3 have non-measurable disease at baseline, the overall response will be derived based on non-target lesion response and/or the emergence of new lesion(s). The exact 2-sided 95% CI based on Clopper-Pearson methodology will be derived for CBR. The null hypothesis will be rejected if at least 10 patients with clinical benefit are observed out of 24 patients in Cohort 3.

The exact 2-sided 95% CI based on Clopper-Pearson methodology will be derived for 6-month PFS rate (Cohort 4). The null hypothesis will be rejected if at least 14 patients observed to remain alive and progression free at 6 months after the start of treatment out of 28 patients who are treated at recommended dose in Cohort 4.

Table 4. Overall Response Assessment with Target/Non-target Lesion and New Lesions

Target Lesions	Non-target Lesions	New Lesions	Overall Response
CR	CR	No	CR
CR	Non-CR/Non-PD or Not all evaluated	No	PR
PR	Non-PD or Not all evaluated	No	PR
SD	Non-PD or Not all evaluated	No	SD
Not all evaluated	Non-PD	No	Not evaluable
PD	Any	Yes or No	PD
Any	PD	Yes or No	PD
Any	Any	Yes	PD

Table 5. Confirmation Rules for Overall Response of PR and CR

Earlier Response	Later Response	Confirmed Response
(to be confirmed)	(confirmation)	
CR	CR	CR
CR	Not CR or missing	SD
PR	CR or PR	PR
PR	SD or PD or missing	SD
PR	SD and then PR (only one SD in between)	PR
SD	n/a – no confirmation needed	SD
PD	n/a – no confirmation needed	PD

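### Protocol 10.1 and SAP 4.3 leave the early-death and toxicity exception out of the response-evaluable definition, so read literally they replace patients whom Table 13 and SAP 5.3 count as non-responders

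*Protocol*

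**What the plan says.** **Sample-size sections.** Protocol 10.1 states that the efficacy patient numbers refer to response-evaluable patients. It spells out that set as treated patients with measurable disease (evaluable disease in Cohort 3), at least one post-baseline assessment and central confirmation of amplification. A treated patient who is not eligible for the set is made good by further enrolment. The examples are a patient whose amplification cannot be confirmed centrally "or no post-baseline tumor assessment is available), additional patients will be enrolled to ensure the correct number of response-evaluable patients". SAP 4.3 repeats this. Protocol 10.1 cites Table 13 for the definition; SAP 4.3 cites nothing.

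**Population definitions.** Protocol Table 13 (section 10.3) gives the same conditions and then adds: "Patients who discontinue due to intolerable toxicity or death prior to the first post-baseline tumor assessment will also be considered evaluable". Such patients are classed as non-responders. SAP 5.3 has the same sentence.

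**Where the set is used.** SAP 6.8 triggers the interim analyses at 19 response-evaluable patients in each of Cohorts 1 and 2 and at 9 in Cohort 3. Protocol 3.1 and SAP 4.1 expand to about 55 and 24 response-evaluable patients. Protocol 10.5.2 puts the primary ORR on the Response Evaluable Set. SAP 6.4 instead uses all treated patients with centrally confirmed amplification, and SAP 6.4.1.1 keeps the Response Evaluable Set for sensitivity analysis.

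**The concern.** The two-stage rules are counts out of fixed numbers of response-evaluable patients, so the definition decides who fills the 19, 55, 9 and 24. A patient who dies or stops for toxicity before any scan cannot be a responder. If that patient is replaced, a certain failure gives way to someone who can still respond. The responder count then tends upward at the stage-1 futility look and against the final cut-off, which is the direction of a false positive. Site or data staff working from the sample-size section alone, particularly in the SAP, would find no exception there.

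**Working it through.** **Inputs from the documents**
- Cohorts 1-2: null ORR 15%, target 30%, "at an approximate 5% 1-sided significance level and 80% power"; continue with at least 4 responders among 19; then "an additional 36 patients will be enrolled, for a total of at least 55 patients per cohort" (Protocol 10.1).
- Cohorts 1-2, final cut-off: the protocol prints none. SAP 6.4.1: "The null hypothesis will be rejected if at least 15 responders observed out of 55 patients".
- Cohort 3: null CBR 25%, target 50%, 5% and 80%; continue with at least 3 of 9; total 24 (Protocol 10.1). Final cut-off at least 11 (Protocol 10.1) or at least 10 (SAP 4.3 and 6.4.1).

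**Assumed inputs**
- *d*, the share of treated, centrally confirmed patients who die or stop for toxicity with no scan at all. Neither document gives it; 5, 10 and 15% are shown.
- All of these patients are replaced.
- The null rates describe all treated, centrally confirmed patients. The documents do not say so.

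**Formulas.** With n1 patients in stage 1, c1 responders needed to continue, n in total and final cut-off c:
- P(pass stage 1) = P(Bin(n1, p) ≥ c1)
- P(reject) = Σ over x ≥ c1 of P(Bin(n1, p) = x) × P(Bin(n − n1, p) ≥ c − x)

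**Reproducing the plan.** A search for Simon's optimal design returns the planned sizes:
- Cohorts 1-2: 19 and 55, continue at 4, reject at 13; type I error 4.77%, power 80.06%.
- Cohort 3: 9 and 24, continue at 3, reject at 10; type I error 4.85%, power 80.55%.

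The stated sizes, error and power therefore reproduce, but the 13 is printed nowhere. As a hand check on Cohort 3 stage 1: P(X ≤ 2) = 0.75⁹ + 9(0.25)(0.75⁸) + 36(0.25²)(0.75⁷) = 0.0751 + 0.2253 + 0.3003 = 0.6007, so 39.9% pass under the null.

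**Effect of full replacement.** Every lost patient is a non-responder, so the null rate among counted patients becomes p0/(1 − d):
- Cohorts 1-2: 0.15/0.95 = 0.158; 0.15/0.90 = 0.167; 0.15/0.85 = 0.176
- Cohort 3: 0.25/0.95 = 0.263; 0.25/0.90 = 0.278; 0.25/0.85 = 0.294

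| Quantity under the null | d = 0 | 5% | 10% | 15% |
|---|---|---|---|---|
| Pass stage 1, Cohorts 1-2 | 31.6% | 35.2% | 39.3% | 43.9% |
| Pass stage 1, Cohort 3 | 39.9% | 43.6% | 47.7% | 52.1% |
| Type I error, Cohorts 1-2, ≥15/55 (SAP) | 1.2% | 1.8% | 2.9% | 4.5% |
| Type I error, Cohorts 1-2, ≥13/55 (unprinted) | 4.8% | 6.7% | 9.3% | 13.0% |
| Type I error, Cohort 3, ≥10/24 (SAP) | 4.9% | 6.6% | 9.0% | 12.3% |
| Type I error, Cohort 3, ≥11/24 (protocol) | 2.0% | 2.9% | 4.2% | 6.1% |

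The d = 0 column is also the result when these patients are counted as Table 13 directs.

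**Thresholds.** Type I error doubles at d = 10.4% (≥13/55), 7.9% (≥15/55), 11.2% (≥10/24) and 9.3% (≥11/24). It stays below 5% until d = 16.2% at ≥15/55 and until d = 12.3% at ≥11/24.

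**Denominator.** At d = 10%, 55 scanned patients correspond to 55/0.90 ≈ 61 treated, confirmed patients. Using the larger denominator lowers the estimated rate but leaves the number of responders unchanged, so a rule stated as a count out of 55 is not corrected by it.

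**The case against.** The strongest reply is that the sections agree when read together. Protocol 10.1 points to Table 13 and replaces only patients who are not eligible for the set; Table 13 makes early deaths and toxicity stops eligible. The example of a missing assessment would still cover withdrawal or loss to follow-up. SAP 6.8 likewise uses a term that SAP 5.3 defines with the exception. This reading is available and is probably what was intended. It does not remove the problem: both sample-size sections write out their own definition without the exception and then offer the unscanned patient as a replacement case without qualification, and SAP 4.3 lacks the citation.

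Three further points limit the size:
- SAP 6.4 keeps these patients in the primary denominator. That protects the estimate and its interval, but not the interim looks or the fixed cut-offs.
- The Schedule of Events requires a tumour assessment at end of treatment, and Protocol 3.2.5 continues scans after a stop without progression. Most toxicity stops should therefore have a scan and be evaluable under either text. The disputed group is those with no scan at all.
- If the null rates were meant for scanned patients only, replacement would not raise the type I error above its design value.

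A reader might infer that the plan requires replacement, that the cohorts would hold only patients who survived and tolerated treatment to a scan, or that the type I error roughly doubles. The documents support none of these as a flat statement. The first two ignore the reconciled reading. The third needs about 8-11% early loss, all of it replaced; at 5% the error rises about 1.4 to 1.5 times.

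**Conclusion.** The inconsistency in the text is real and appears in both documents. Its effect is conditional on three things: the literal reading of Protocol 10.1 and SAP 4.3 being followed, an early-loss rate that neither document gives, and null rates that apply to all treated, centrally confirmed patients. Under those assumptions, 5-15% early loss raises the null chance of passing stage 1 by about 4 to 12 percentage points in each of Cohorts 1-3, whatever the final cut-off.

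The effect on type I error depends on which cut-off applies. At the SAP's 15/55 it stays below 5% throughout the assumed range, but only because that cut-off is stricter than the stated 5% design. At 13/55, or at the SAP's 10/24, it exceeds 5% across the range. At the protocol's 11/24 it exceeds 5% only above 12.3% loss. The differences between the cut-offs are a separate matter. So is the handling of patients left unscanned for other reasons, such as clinical progression.

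**What to change.** In Protocol 10.1 and SAP 4.3:
- Replace the shortened definition with the full one from Table 13 and SAP 5.3.
- Limit the replacement example to patients who lack a post-baseline assessment for reasons other than death or intolerable toxicity.
- State that early deaths and toxicity stops count toward the 19, 55, 9 and 24 as non-responders, at both the stage-1 look and the final count.

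The cost is a sentence or so in each document. The observed response or benefit rate may be slightly lower. No extra patients are needed, since fewer are replaced. That also suits the planned total of 168, which equals 55 + 55 + 24 + 34 and leaves no allowance for replacements.

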4.3. Determination of Sample Size

Approximately 168 patients in total may be enrolled in the study.

Please note: the patient numbers given for efficacy analysis are for the response-evaluable population, defined as the subset of treated patients who have measurable disease (or evaluable disease in Cohort 3), who have at least 1 post-baseline disease/tumor assessment, and who have centrally confirmed *FGFR* amplification. If a treated patient is not eligible for the response-evaluable population (for example, because *FGFR* amplification cannot be centrally confirmed or no post-baseline tumor assessment is available), additional patients will be enrolled to ensure the correct number of response-evaluable patients for analysis as described below.

Sample size considerations for **Cohorts 1 and 2** (primary endpoint ORR) are based on a 2-stage Optimal Simon design, comparing a poor response of \leq 15% versus a promising response of \geq 30%, at an approximate 5% 1-sided significance level and 80% power.

- In Stage 1 (futility assessment), enrollment will include 19 patients in each cohort and accrual will continue to Stage 2, if at least 4 (21%) of 19 patients respond (CR or PR).
- In Stage 2, if the Stage 1 futility boundary is exceeded, an additional 36 patients will be enrolled, for a total of at least 55 patients per cohort. In Cohorts 1 or 2, with a total of 55 patients, if the observed ORR is 30.9%, the 95% exact confidence interval (CI) is (19.1%, 44.8%).

Sample size considerations for **Cohort 3** (primary endpoint CBR) are also based on a 2-stage Optimal Simon design. The null hypothesis that the true CBR is 25% will be tested against a 1-sided alternative, which yields a type I error rate of 5% and power of 80% when the true CBR rate is 50%. In the first stage, 9 patients will be treated. If there are \leq 2 patients with clinical benefit (ie, CR or SD \geq 24 weeks) in these 9 patients, the cohort will be discontinued. Otherwise, 15 additional patients will be treated for a total of 24 patients. The null hypothesis will be rejected if \geq 10 patients with clinical benefit are observed in 24 patients.

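### Cohort 3's rejection cut-off is 11 of 24 in the protocol and 10 of 24 in the SAP; only 10 delivers the stated 5% type I error and 80% power.

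*Protocol*

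**What the plan says.** Protocol Section 10.1 states that the Cohort 3 sample size considerations ("primary endpoint CBR) are also based on a 2-stage Optimal Simon design") rest on these terms: "The null hypothesis that the true CBR is 25% will be tested against a 1-sided alternative". The claimed operating characteristics are 5% for the type I error and, at a CBR of 50%, 80% for the power. On enrolment it says "In the first stage, 9 patients will be treated"; the cohort stops if 2 or fewer of them benefit, and otherwise 15 more are added for a total of 24. The null is then rejected at or above "11 patients with clinical benefit are observed in 24 patients". The Synopsis (Statistical Methods) repeats the same text with the same cut-off of 11.

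SAP Section 4.3 repeats every design input unchanged, but rejects at or above "10 patients with clinical benefit are observed in 24 patients". SAP Section 6.4.1 restates this as the analysis rule: "The null hypothesis will be rejected if at least 10 patients with clinical benefit are observed out of 24 patients in Cohort 3".

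SAP Section 7 says that nothing has changed from the initially planned analyses.

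**The concern.** The two documents share every input to the design and differ only in the number that decides the primary endpoint. A given set of rates, stage sizes and futility bound has one type I error and one power for each cut-off, so 10 and 11 cannot both yield the 5% and 80% that both documents claim.

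Two things are at stake. First, a result of exactly 10 of 24 would give opposite primary conclusions depending on which document is followed. The study is open-label and the sponsor reviews the data itself, so settling the matter after that result is known would be a post hoc choice. Second, if 11 is the operative rule, the cohort has less power than the protocol tells investigators and ethics committees it has.

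**Working it through.** **Inputs** (Protocol Section 10.1, the same in SAP Section 4.3): null rate p0 = 0.25, target rate p1 = 0.50, stage 1 n1 = 9, stop if 2 or fewer, stage 2 n2 = 15, total n = 24. Cut-off c = 11 (protocol) or c = 10 (SAP).

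**Formula.** The null is rejected only if the cohort passes stage 1 and the total reaches c:

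P(reject | p) = Σ over x = 3 to 9 of P[Bin(9, p) = x] × P[Bin(15, p) ≥ c − x]

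Type I error is this value at p = 0.25, and power is its value at p = 0.50.

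**Power under the protocol's rule, c = 11, p = 0.50:**

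| Stage 1 benefits x | P(x of 9) | Needed in stage 2 | P(that many or more of 15) | Product |
|---|---|---|---|---|
| 3 | 0.1641 | 8 | 0.5000 | 0.0820 |
| 4 | 0.2461 | 7 | 0.6964 | 0.1714 |
| 5 | 0.2461 | 6 | 0.8491 | 0.2090 |
| 6 | 0.1641 | 5 | 0.9408 | 0.1543 |
| 7 | 0.0703 | 4 | 0.9824 | 0.0691 |
| 8 | 0.0176 | 3 | 0.9963 | 0.0175 |
| 9 | 0.0020 | 2 | 0.9995 | 0.0020 |
| **Sum** | | | | **0.7053** |

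With c = 10, each row needs one fewer stage 2 benefit. The products become 0.1142, 0.2090, 0.2315, 0.1612, 0.0700, 0.0176 and 0.0020, and they sum to 0.8055.

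**Both error rates for neighbouring cut-offs:**

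| Reject at | Type I error (p = 0.25) | Power (p = 0.50) |
|---|---|---|
| 9 or more | 0.1001 | 0.8659 |
| 10 or more | 0.0485 | 0.8055 |
| 11 or more | 0.0199 | 0.7053 |
| 12 or more | 0.0069 | 0.5689 |

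Only 10 satisfies both stated targets. The protocol's pair of 5% and 80% is reproduced at 10 and not at 11, where power is short by 0.80 − 0.7053 = 0.0947. With 11, power reaches 80% only when the true CBR is about 53%.

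**Does a different reading rescue 11?** Ignoring the interim look and treating the test as a single stage with n = 24, a cut-off of 11 gives type I error 0.0213 and power 0.7294. That is still about 7 points short.

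**Which design was meant?** I searched all two-stage designs with total size 10 to 35, type I error at most 0.05 and power at least 0.80, for the smallest expected sample size under the null. The search returns n1 = 9, stop at 2 or fewer, n = 24, reject at 10 or more. Its probability of early stopping under the null is 0.601, so the expected size is 9 + 0.399 × 15 = 14.99. This matches the protocol's design in every number except the final cut-off.

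**How often the documents would disagree.** They differ only when the cohort passes stage 1 and ends at exactly 10. The probability is the difference between adjacent rows of the second table: 0.0485 − 0.0199 = 0.029 at a true CBR of 25%, and 0.8055 − 0.7053 = 0.100 at 50%.

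**The case against.** Four points can be made for leaving this alone or for treating it as minor.

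- **The SAP governs.** Protocol Sections 10 and 10.5.2 leave analysis detail to the SAP, which says 10 in both places, so a statistician following it would apply the right rule. This lowers the practical risk. But neither document states an order of precedence, and SAP Section 7 denies any change, so the conflict is not settled in writing.
- **The effect is narrow.** The documents disagree at one outcome, in a small open-label cohort, and Protocol Section 10.5.2 says efficacy will be summarized descriptively. The narrowness is real and is quantified above. Both documents nonetheless state a formal rejection rule with error rates.
- **Eleven may have been deliberate.** The planned two-sided 95% Clopper-Pearson interval has a lower limit of 22.1% at 10/24 and 25.6% at 11/24, so 11 is the smallest count whose interval excludes the 25% null. The SAP's cut-off of 15/55 for Cohorts 1 and 2 has the same property: the lower limit is 14.7% at 14 and 16.1% at 15, against a null of 15%. This is the strongest objection. Neither document gives it as the reason, however, and it would not make the stated 80% power true. What stands is that at exactly 10 of 24 the test would reject while the reported interval contains 25%, and the plan should say so.
- **The analysed number may not be 24.** Protocol Section 10.1 sizes the cohort on response-evaluable patients, while SAP Section 6.4 analyses treated patients with centrally confirmed amplification. With 26 analysed (17 in stage 2), a cut-off of 10 has type I error 0.076. This is a fair limit on what any fixed cut-off guarantees, but it is a separate matter and does not reconcile 10 with 11.

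**Conclusion.** The concern holds. The protocol's cut-off of 11 contradicts both SAP statements and the protocol's own error rates: it gives type I error 0.0199 and power 0.7053, against 0.0485 and 0.8055 at 10. The stated inputs identify 10 as the cut-off of the design described. These figures assume exactly 24 analysed patients, independent outcomes with a common benefit probability, and binding application of the stage 1 stopping rule. Why the protocol has 11 cannot be determined from the documents. Because this is the decision rule for a primary endpoint, it should be corrected before Cohort 3 results are known.

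**What to change.** Change the Cohort 3 cut-off from 11 to 10 in the Protocol Synopsis (Statistical Methods) and in Section 10.1. SAP Sections 4.3 and 6.4.1 then stand as written. Sample size, the stage 1 rule and patient treatment are unaffected.

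Add one sentence to SAP Section 6.4.1 saying that the decision rests on the one-sided two-stage rule and that the two-sided 95% interval is descriptive, so that a result of 10 of 24 (lower limit 22.1%) is not read as self-contradictory.

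The cost is one number in two places of a protocol amendment and one SAP sentence. Relative to a cut-off of 11, the attained type I error rises from 2.0% to 4.9%, which is within the 5% already stated. If the sponsor did intend 11, the correction runs the other way: both SAP sections must change to 11, and both documents must restate the operating characteristics as about 2.0% type I error and 70.5% power.
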